6.1.2 DOSING AND ADMINISTRATION

The study intervention consists of a bolus loading dose followed by a continuous infusion. For patients in the intervention group, the bolus loading dose will consist of ketamine 0.5 mg/kg administered intravenously over 10 minutes (or over 20 minutes if BMI > 40). This will be followed by a continuous infusion at 0.3 mg/kg/h for an additional 2 hours 50 minutes.

Patients in the control group will receive an equal volume of normal saline. The bolus loading dose will consist of normal saline 0.1 mL/kg administered intravenously over 10 minutes (or over 20 minutes if BMI > 40). This will be followed by a continuous infusion at 0.06 mL/kg/h for an additional 2 hours 50 minutes.

Study intervention dosing will be based on actual body weight.

Timing of study medication administration will be the same for both groups. For patients who are extubated in the operating room, the study medication will be initiated prior to leaving the operating room. For patients who remain intubated and transfer to the intensive care unit, the study medication will be administered based on the following criteria:

- If the patient is extubated before 07:00am on postoperative day 1, the study medication will be administered between 05:00am and 08:00am on postoperative day 1.
- If the patient is extubated after 07:00am on postoperative day 1 and before 07:00am on postoperative day 2, the study medication will be administered between 05:00am and 08:00am on postoperative day 2.
- If the patient is extubated after 07:00am on postoperative day 2 and before 07:00am on postoperative day 3, the study medication will be administered between 05:00am and 08:00am on postoperative day 3.
- If the patient remains intubated at 07:00am on postoperative day 3, the patient will be withdrawn from the study.

In the operating room, the study medication will be administered by the anesthesiology clinician (MD or certified registered nurse anesthetist). In the PACU or ICU, the study medication will be administered by the patient's bedside nurse.

Richmond Agitation and Sedation Scale (RASS) scores will be monitored per standard nursing protocols, as described in section 8.2. If the patient experiences sedation to a RASS score ≤ -2 , then the study medication will be halted and the procedures documented in section 7.1 will be followed.

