6.5 CONCOMITANT THERAPY

Intraoperatively, enrolled participants should not receive open-label ketamine. Otherwise, all components of the anesthetic care plan will be at the discretion of the attending anesthesiologist.

Postoperatively, enrolled participants should not receive open-label ketamine. During the study medication infusion, concurrent infusions of propofol, midazolam, or other sedative agents with GABA receptor activity will not be permitted. Concurrent dexmedetomidine is permitted. During the study medication infusion, administration of benzodiazepines or gabapentin will not be permitted. All other components of postoperative care will occur as directed by the clinical team.

Medications administered to the patient will be retrieved by the research team from the electronic health record. In particular, administrations of the following medication classes between 05:00am on the day of the study medication infusion and 06:00am on post-infusion day 2 will be retrieved:

- Benzodiazepines
- Anticonvulsants
- Alpha agonists (dexmedetomidine, clonidine)
- Hypnotic agents
- Antihypertensive agents
- Antiarrhythmic agents

Administrations of the following medication classes between 06:00am on the day of the study medication infusion and 06:00am on post-infusion day 7 will be retrieved:

- Opioid analgesics
- Non-opioid analgesics
- Antiemetics

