8 STUDY ASSESSMENTS AND PROCEDURES

8.1 EFFICACY ASSESSMENTS

Depressive Symptom Measurement

Depressive symptoms will be measured using the Montgomery-Asberg Depression Rating Scale (MADRS) preoperatively and on post-infusion days 1, 2, 4, 7, and 14. The MADRS rates the severity of 10 depressive symptoms based on a targeted clinical interview, yielding a total score 0 (no symptoms) and 60 (severe symptoms).^{49,50} The scale has been found to correlate highly with a global clinician assessment (Pearson correlation = 0.71)⁵¹ and to have high inter-rater reliability.⁴⁹ The MADRS has been modified to assess symptoms over the previous day rather than the previous week.^{36,37} This modified version will be used on the post-infusion days.

The MADRS will be administered by a trained research team member. Post-infusion assessments will be conducted between 07:00am and 12:00pm approximately on the specified days. The time of day for the preoperative assessment will be variable, depending on the time of the patient's CPAP appointment or in-hospital visit. If the patient is discharged from the hospital before the day of the final study assessment, the MADRS will be conducted over the telephone.

Concurrent with each MADRS assessment, the research team member will use the Clinical Global Impression (CGI) to rate the overall severity of the patient's mental illness.⁵² At each postoperative follow-up, the CGI will also be used to rate the overall level of improvement compared to the previous assessment.

Concurrent with each MADRS assessment, self-reported depressive symptoms will be collected using the Quick Inventory of Depressive Symptomatology (QIDS).⁵³

The MADRS includes questions about suicidal ideation. If the patient reports any suicidal ideation, then the Suicide Risk Management Protocol will be initiated. This includes a structured assessment allowing stratification of the risk for self-harm, notification of the principal investigator, and (if risk is moderate or high) notification of an on-call psychiatrist.

Electroencephalogram (EEG) Measurement

EEG will be captured using the Dreem headband (DREEM, Rhythm, New York, NY), a consumer-grade wireless device using dry electrodes. The device uses five EEG channels (F7, F8, FpZ, O1, O2), accelerometry, and pulse oximetry. It samples EEG electrode potentials at a rate of 250 Hz and applies a 0.4-30 Hz bandpass filter.

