Safety events will include significant hypertension during the infusion, defined as systolic blood pressure > 180 mmHg or the administration of an antihypertensive medication that is not one of the patient's home medications. Another safety event will be tachycardia, defined as heart rate > 100 beats per minute, during the infusion.

Nausea and Vomiting

At each post-infusion study visit, participants will be asked if they have experienced nausea or vomiting in the past 24 hours. If present, the patient will be asked to classify the event as mild, moderate, or severe. In addition, the electronic medical record will be reviewed for administration of antiemetic medication.

Baseline Factors Potentially Related to Depression

At the time of enrollment, the patient will complete several surveys evaluating factors that may be related to their depressive history or that may predict treatment responsiveness. These surveys will include the Generalized Anxiety Disorder 7-item scale (GAD-7),⁵⁷ the Alcohol Use Disorders Identification Test (AUDIT),⁵⁸ the Drug Abuse Screening Test (DAST-10),⁵⁹ and the Childhood Trauma Questionnaire (CTQ).⁶⁰

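### For ICU patients infused from 05:00, the 24-hour nausea question covers at most one of three infusion hours and antiemetic retrieval misses the first, and section 9.4.4 does not say which source or window counts

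*Combined protocol and SAP*

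**What the plan says.** All references are to the combined protocol and SAP.

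- **Nausea question (section 8.2).** At each post-infusion visit "participants will be asked if they have experienced nausea or vomiting in the past 24 hours". In addition, "the electronic medical record will be reviewed for administration of antiemetic medication"; no time limit is attached to that review.
- **Infusion time, ICU route (section 6.1.2).** For a patient extubated before 07:00 on the first postoperative day, "the study medication will be administered between 05:00am and 08:00am on postoperative day 1". The same clock times apply on postoperative days 2 and 3. Patients extubated in the operating room start study drug before leaving it.
- **Visit time (section 8.1).** "Post-infusion assessments will be conducted between 07:00am and 12:00pm approximately on the specified days". This is written for the depression rating.
- **Drug retrieval (section 6.5).** Antiemetics and analgesics given "between 06:00am on the day of the study medication infusion and 06:00am on post-infusion day 7 will be retrieved". The other list (benzodiazepines, antihypertensives and others) covers drugs given "between 05:00am on the day of the study medication infusion and 06:00am on post-infusion day 2 will be retrieved".
- **Analysis (section 9.4.4).** The number of patients who report nausea and vomiting is compared between arms by chi-square test. No source and no time window is named. The checklist side effects during the infusion are analysed as a separate item.

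**The concern.** Section 2.3.1 lists nausea and vomiting as an immediate risk of ketamine. Section 9.4.4 plans a between-arm comparison of it, and section 10.1.6 puts it before the independent safety monitor as its own item. One would expect the measure to include the time when drug is running, as those for hypertension and tachycardia do: both are defined during the infusion.

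The nausea question is tied to the visit instead. On the ICU route the infusion is early in the morning and the visit is later in the morning of the next day, so a 24-hour look-back tends to begin after the infusion has ended. On the operating-room route the infusion usually starts later in the day and falls inside the look-back. A single pooled incidence would then count infusion-time nausea for one route and mostly omit it for the other. The antiemetic record, which might fill the gap, is pulled from one hour after the earliest ICU start.

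**Working it through.** **Inputs**

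- Planned duration (section 6.1.2): 10 min load + 2 h 50 min = 3 h 00 min, which reproduces the 3 planned hours stated in section 9.4.2. With BMI above 40: 20 min + 2 h 50 min = 3 h 10 min.
- ICU clock times: 05:00 to 08:00 (section 6.1.2).
- Visit clock time *t*: 07:00 to 12:00, approximate (section 8.1). That the nausea question is asked at the same visit is an assumption.
- Post-infusion day 1 is the day after the infusion. Section 8.1 lists the night after the infusion separately from the night after post-infusion day 1.
- Antiemetic retrieval starts at 06:00 on the infusion day (section 6.5).

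**Formulas.** Let the infusion start at S, end at E and last L = E − S. A 24-hour look-back from time *t* on day 1 begins at time *t* on the infusion day, so:

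- recall coverage = min(L, max(0, E − *t*)) / L
- antiemetic coverage = (E − max(S, 06:00)) / L

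**Infusion run 05:00 to 08:00 (L = 3 h)**

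- Visit at 07:00: 08:00 − 07:00 = 1 h; 1/3 = 33%.
- Visit at 07:30: 0.5 h; 0.5/3 = 17%.
- Visit at 08:00 or later: 0 h.
- If visit times are uniform over the 5-hour window (an assumption), mean coverage is (½ × 1 h × 1 h)/5 h = 0.1 h, or 0.1/3 = 3%, and 4/5 = 80% of visits cover none of the infusion.
- Antiemetics: 08:00 − 06:00 = 2 h; 2/3 = 67%. The missed hour, 05:00 to 06:00, contains the whole load (05:00 to 05:10, or 05:20 with BMI above 40).

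**BMI above 40, 05:00 to 08:10 (L = 190 min).** Recall at a 07:00 visit: 70/190 = 37%. Mean over uniform visits: 4%. Antiemetics: 130/190 = 68%.

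**If 05:00 to 08:00 is a window for starting (L = 3 h)**

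| Start | End | Antiemetics | Recall, 07:00 visit | Recall, 09:30 visit | Recall, 12:00 visit | Mean recall, uniform visits |
|---|---|---|---|---|---|---|
| 05:00 | 08:00 | 67% | 33% | 0% | 0% | 3% |
| 06:00 | 09:00 | 100% | 67% | 0% | 0% | 13% |
| 07:00 | 10:00 | 100% | 100% | 17% | 0% | 30% |
| 08:00 | 11:00 | 100% | 100% | 50% | 0% | 50% |

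**Operating-room route.** By the same formula, the look-back covers the whole infusion whenever it starts no earlier in the day than the clock time of the next day's visit. The documents give no distribution of operating-room start times. For infusions begun after surgery of at least 2 hours this will usually hold, though not always for a late-morning visit.

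**Recall needed to reach a 05:00 start.** From a 07:00 visit: 24 + 2 = 26 h. From a 12:00 visit: 24 + 7 = 31 h.

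**The case against.** A reader might infer that nausea during the ICU infusion goes largely unrecorded in this trial. The documents do not support that, for these reasons:

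- Section 8.2 has the Clinical and Adverse Events Checklist given about 1 to 2 hours after the load begins, and section 9.4.4 compares each of its side effects between arms. Its items are not in the documents, so whether it asks about nausea is unknown.
- Section 8.3.4 requires an adverse event inquiry at each visit covering all time since the previous one, with time of onset recorded.
- Antiemetic retrieval covers two thirds of a 05:00 to 08:00 infusion. Section 6.5 also opens with a general statement that administered drugs will be retrieved, and the record review in section 8.2 has no time limit, so the first hour might be picked up anyway.
- The clock times can be read as a window for starting. A 3 h 10 min infusion cannot fit inside 05:00 to 08:00, and halts and restarts under section 7.1 would push the end later.

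All of this stands, and it limits the point to the dedicated nausea measure. It does not remove the point. Section 9.4.4 counts patients who report the symptom and sends other adverse events to section 8.3; nothing says that the checklist, the adverse event inquiry or antiemetic use enters the nausea count. Even if the checklist includes nausea, it precedes the last 1 to 2 hours of the infusion and is next given on day 14. Antiemetic use is only a proxy: it may be prophylactic, and untreated nausea leaves no record.

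A reader might also infer bias towards one arm. The windows are the same in both arms, and delivery route is settled before randomization (section 6.3), so the effect is lost sensitivity.

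Finally, five 24-hour look-backs cover only 5 of 14 days (36%). That says nothing about capture during the infusion, and with the beta half-life of about 2.3 hours given in section 4.3, the later gaps are remote from exposure.

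**Conclusion.** The point holds for the dedicated nausea and vomiting measure on the ICU route. With the infusion at 05:00 to 08:00, the question covers 0 to 1 of 3 infusion hours, and antiemetic retrieval covers 2 of 3, out of step with the 05:00 start of the other list in section 6.5. If the clock times mark a window for starting, an 08:00 start gives full antiemetic coverage and 0 to 100% recall coverage, so capture depends on when the visit happens to take place.

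The consequence is a between-arm comparison that can lose sensitivity equally in both arms and that pools two exposure windows. How much this matters depends on the share of ICU-route patients, which the documents do not give. The result rests on the nausea question being asked at the 07:00 to 12:00 visit; the 3% and 80% figures also assume uniform visit times. Nausea is neither a primary nor a secondary endpoint, and other sources may hold the same events, so this is a minor reconciliation.

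**What to change.** 1. **Section 8.2.** At the post-infusion day 1 visit, ask about nausea or vomiting 'since the study infusion started'. Changing the recall period at later visits is optional.
2. **Section 6.5.** Start antiemetic and analgesic retrieval at the recorded start of the infusion, or at 05:00 to match the other list.
3. **Section 9.4.4.** State that nausea incidence is counted from the start of the infusion, and name the sources that count (the visit question, the checklist, adverse event reports, antiemetic use).

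Section 6.1.2 should also make clear whether 05:00 to 08:00 bounds the whole infusion or only its start, since the 3 h 10 min case does not fit the first reading.

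The cost is the wording of one question, one data-pull time and a sentence or two in the analysis section. The downside is longer recall at day 1 for a 05:00 ICU start: 26 to about 31 hours instead of 24.

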5.5 STRATEGIES FOR RECRUITMENT AND RETENTION

Anticipated Patient Population – The target sample size will be 32 patients. Patients will be enrolled at a single site (BJH/Washington University School of Medicine). The expected accrual rate was estimated by examining characteristics (obtained via Epic Slicer Dicer at the population level only) of a retrospective cohort of patients who had non-emergent surgery at BJH between 1/1/2021 and 6/30/2021, had an ICU admission, and had an ICD grouper corresponding to depression documented in the diagnosis list or the past medical history. The query was limited to the cardiac, neurosurgery, and vascular services because many of the patients from other services (e.g., trauma, orthopedic) were suspected to have initially had emergent surgery followed by an ICU admission and then a non-emergent surgery. Exclusion criteria for the retrospective query included age < 18. During that 6-month time period, there were 307 patients who met these criteria (Figure 2). If we conservatively estimate that 20% of these patients enroll in the trial, that results in an accrual of 10 patients per month.

The gender, race and ethnicity, and age distributions are expected to follow the gender, race and ethnicity, and age distributions served by the Barnes-Jewish Hospital. These distributions were observed in the retrospective cohort seen in Figure 2. The anticipated characteristics of the study population are shown in Table 1.

[figure not shown]

Figure 2. Number of potentially eligible patients in a 6-month period.

Table 1. Anticipated Demographic Characteristics of the Study Population

Racial Categories	Ethnic Categories				Total	
	Not Hispanic or Latino		Hispanic or Latino			
	Female	Male	Female	Male		

American Indian/ Alaska Native	1	0	0	0	1
Asian	1	0	0	0	1
Native Hawaiian or Other Pacific Islander	0	0	0	0	0
Black or African American	2	2	0	0	4
White	13	11	1	1	26
More than One Race	0	0	0	0	0
Total	17	13	1	1	32

Recruitment Strategy – Patients will primarily be recruited at the Center for Preoperative Assessment and Planning (CPAP). Potentially eligible patients will be identified by screening the CPAP schedule. Patients identified via screening will be approached by telephone prior to their CPAP appointment or in person at CPAP.

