9.4 STATISTICAL ANALYSES

9.4.1 GENERAL APPROACH

For descriptive statistics, categorical data will be presented using frequency counts and percentages, normally distributed continuous data will be presented using means and standard deviations, and non-normally distributed continuous data will be presented using medians and interquartile ranges.

Normality will be assessed using visual analysis of histograms and using the Kolmogorov-Smirnov test. All inferential tests will be two-tailed, and p-values < 0.05 will be considered statistically significant.

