9.4.4 SAFETY ANALYSES

Psychotomimetic Symptoms:

The BPRS four-item positive symptom subscale score and the CADSS-6 score will be calculated for each patient. The distribution of scores will be assessed for normality using visual analysis of histograms and using the Kolmogorov-Smirnov test. If the scores are normally distributed, then the mean score in the two groups will be compared using a two-sample t-test. If the scores are not normally distributed, then the median score in the two groups will be compared using a Wilcoxon rank sum test.

Clinical and Adverse Events Checklist:

The number of patients reporting each side effect during the study medication infusion will be determined. The incidence of each side effect will be compared between the two groups using a chi-square test (or using a Fisher exact test in the case of rare side effects).

Significant Hypertension during Infusion:

The number of patients experiencing a systolic blood pressure > 180 mmHg during the study medication infusion or receiving an antihypertensive medication during the infusion that is not on the patient's home medication list will be determined. The incidence of significant hypertension will be compared between the two groups using a chi-square test.

Tachycardia during Infusion:

The number of patients experiencing a heart rate > 100 beats per minute during the study medication infusion will be determined. The incidence of tachycardia will be compared between the two groups using a chi-square test.

Nausea and Vomiting:

The number of patients reporting nausea and vomiting will be determined. The incidence of nausea and vomiting will be compared between the two groups using a chi-square test.

Other adverse events will be coded and reported as described in section 8.3.

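### Nausea and vomiting are graded by severity, but the planned between-arm test uses only yes/no incidence and so cannot detect a shift in severity when incidence is similar in both arms

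*Combined protocol and SAP*

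**What the plan says.** Section 8.2, under Nausea and Vomiting, sets out three pieces of data collection. The symptom is asked about repeatedly: "At each post-infusion study visit, participants will be asked if they have experienced nausea or vomiting in the past 24 hours". It is then graded: "If present, the patient will be asked to classify the event as mild, moderate, or severe". Drug treatment is looked up as well: "In addition, the electronic medical record will be reviewed for administration of antiemetic medication". Section 6.5 lists antiemetics among the drug classes whose administrations up to "06:00am on post-infusion day 7 will be retrieved".

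Section 9.4.4 gives nausea and vomiting two sentences: "The number of patients reporting nausea and vomiting will be determined" and "The incidence of nausea and vomiting will be compared between the two groups using a chi-square test". Its closing line sends only other adverse events to section 8.3. The subgroup section (9.4.7) covers the feasibility endpoints, and the exploratory section (9.4.9) covers pain and length of stay. None of these names the nausea grade or antiemetic use.

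Section 9.4.1 sets the testing rule: "All inferential tests will be two-tailed, and p-values < 0.05 will be considered statistically significant". On size, section 5.5 states: "The target sample size will be 32 patients". Allocation is 1:1 (section 6.3).

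**The concern.** A graded answer is collected and then cut to present or absent before the arms are compared. Patients in both arms have just had surgery, so some nausea may occur in either arm whatever the study drug. If ketamine mainly makes nausea worse, rather than making more patients nauseated, the yes/no split falls where the arms differ least.

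The plan handles neighbouring items differently. In 9.4.4 the psychotomimetic scores keep their scale and may be compared by rank sum test. For hypertension, giving a new antihypertensive counts as part of the event. For nausea, neither the grade nor the drug record has a stated use.

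The stake is what the full-scale trial learns about tolerability. Section 2.3.1 lists nausea and vomiting as immediate ketamine risks. A report that incidence was similar could be read as saying nausea was similar.

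**Working it through.** **Inputs from the documents.** 32 patients, 1:1, so 16 per arm; two-sided 0.05; four ordered grades (none, mild, moderate, severe). The documents state no nausea rate, effect size or power for this item, so there is no plan figure to reproduce. All grade distributions below are assumptions.

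**Step 1: why the yes/no test is blind to severity.** With a and b patients reporting any nausea, out of n per arm, the Pearson statistic is

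X² = 2n·[a(n−b) − b(n−a)]² / [n²·(a+b)·(2n−a−b)].

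The grades do not appear in it. If the probability of any nausea is the same in both arms, the rejection rate is simply the size of the test, whatever happens among mild, moderate and severe.

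**Step 2: a worked example.** Take none/mild/moderate/severe counts of 4/9/3/0 on control and 4/2/5/5 on ketamine.

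- Planned analysis: 12/16 versus 12/16, X² = 0, p = 1.00.
- Moderate or severe: 3/16 versus 10/16. X² = 32·(3·6 − 10·13)² / (16²·13·19) = 401,408/63,232 = 6.35, p = 0.012 (Fisher p = 0.029).
- Probability of a worse grade on ketamine, counting ties as half: of 16 × 16 = 256 pairs, ketamine is worse in 2·4 + 5·13 + 5·16 = 153 and tied in 4·4 + 2·9 + 5·3 = 49, so (153 + 24.5)/256 = 0.69. Wilcoxon p = 0.052.

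**Step 3: rejection rates by simulation.** 16 per arm, 6,000 trials per row, uncorrected chi-square and tie-corrected Wilcoxon. Mixes are none/mild/moderate/severe in percent.

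| Control | Ketamine | Yes/no chi-square | Wilcoxon on grades | Chi-square on moderate-or-severe |
|---|---|---|---|---|
| 40/40/15/5 | 40/10/30/20 | 5% | 17% | 45% |
| 60/26/11/3 | 60/8/16/16 | 5% | 8% | 25% |
| 40/36/18/6 | 40/12/24/24 | 5% | 14% | 30% |
| 20/56/20/4 | 20/24/32/24 | 5% | 32% | 48% |
| 50/30/15/5 | 30/20/25/25 | 21% | 40% | 44% |
| 70/20/8/2 | 40/20/20/20 | 41% | 53% | 55% |
| 70/18/9/3 | 50/30/15/5 | 21% | 20% | 9% |

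The first four rows have equal incidence and worse severity on ketamine. The next two raise both. The last raises incidence only, with the severity mix among affected patients unchanged. With no difference between arms (40/36/18/6 in both), the yes/no and Wilcoxon tests reject about 5% of the time.

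**Step 4: why the rank test gains only modestly in the first row.** The probability of a worse grade on ketamine is 0.10·0.40 + 0.30·0.80 + 0.20·0.95 = 0.47, plus half the ties, ½(0.16 + 0.04 + 0.045 + 0.01) = 0.1275, giving 0.60. That is not far from 0.5, and 16 per arm estimates it imprecisely.

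**The case against.** A reader might infer that worse nausea on ketamine would go unseen in this trial. The documents do not support that. The grades are recorded. Section 8.3.4 requires adverse events to be captured with the clinician's assessment of severity and with changes in severity documented. Under section 10.1.6 the independent safety monitor reviews nausea and vomiting every six months. Section 9.4.1 says categorical data will be presented as counts and percentages, which could be read to cover a table of grades. The gap is in the between-arm comparison that 9.4.4 specifies.

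A reader might also infer that mild nausea will be common in both arms. Section 2.3.1 names the risk but gives no rate, so that remains an assumption.

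Three further objections have force. First, the advantage of the rank test depends on the scenario: in the last row of the table it gains nothing. Second, even where it helps it usually misses. At 17% it fails in 83% of trials, and a moderate-or-severe split does better in every equal-incidence row. That split loses badly when only incidence rises (9% against 21%), so it is no safe replacement either. Third, a rank test at each of the five visits (days 1, 2, 4, 7 and 14) would raise a multiplicity problem: with independent tests the chance of at least one false positive is 1 − 0.95⁵ = 0.23, and less if they are positively correlated. A single per-patient summary avoids this.

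Finally, the sample size was chosen for precision of the feasibility proportions (section 9.2), and the plan disclaims power even for its secondary endpoints. Rejection rates are therefore a limited yardstick here. This keeps the point minor but does not remove it: no section states how the grade or the antiemetic record will be used.

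**Conclusion.** The point holds as a minor improvement to section 9.4.4. The planned comparison of nausea and vomiting has no sensitivity to a change in severity at equal incidence; that follows from the form of the test and needs no assumption. How much is lost in practice does need assumptions. With equal incidence and worse severity, the mixes tried give about 5% for the planned test against 8% to 32% for a rank test. When incidence rises as well, the planned test keeps part of its power. When only incidence rises, nothing is lost.

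The calculations assume 16 analysed patients per arm and one grade per patient. Section 9.4.4 does not say how up to five 24-hour recalls become one answer, and either test needs that definition. An ever/never rule can only raise any-nausea incidence in each arm relative to a single visit, which could make the yes/no cut less informative.

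**What to change.** In section 9.4.4:

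1. Define each patient's worst grade (none, mild, moderate, severe) of nausea or vomiting over the post-infusion visits, and say how missed visits are handled.
2. Tabulate worst grade by arm. Compare it once with the Wilcoxon rank sum test that the plan already uses elsewhere, and report the probability of a worse grade on ketamine with a 95% interval.
3. Keep any-nausea incidence, and add the proportion with moderate-or-severe nausea, as descriptive lines with intervals. Show per-visit grades descriptively only, without tests.
4. Report the number of patients given an antiemetic, by arm. State whether counting starts with the study medication: the retrieval window in 6.5 opens at 06:00 that day and can include doses given earlier, for example during surgery in patients extubated in the operating room.

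The cost is a few sentences and a few table rows, from data already collected. Power remains low at 32 patients, so the by-arm table and the interval should carry the interpretation, not the p-value.
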